¹⁷ Subjects will be observed during infusion and at least 2 hours after completing the infusion of VIS410 to allow monitoring for possible hypersensitivity reactions. VIS410 will be administered over 2 hours. Infusion time can be extended at discretion of the Investigator up to 4 hours based on local infusion-related symptoms. If any serious systemic reactions occur, the infusion of VIS410 can be slowed or stopped at the discretion of the Investigator.

¹⁸ Within 1 hour prior to VIS410 administration.

¹⁹ Sample collected within 30 minutes after completing the infusion of VIS410/placebo.

²⁰ Nasopharyngeal swabs will be obtained from both nostrils (1 swab per nostril).

²¹ Will be done for the first 50 subjects enrolled only.

²² If a subject presents with or reports influenza-like illness, additional swabs (1 swab per nostril) should be taken (see Section 7.1.5).

LIST OF ABBREVIATIONS AND DEFINITIONS OF TERMS

Abbreviation	Definition
ADA	Anti-drug antibody
AE	Adverse event
AESI	Adverse event of special interest
AUC	Area under the curve
AUC _{0-∞}	Area under the concentration-time curve extrapolated to infinity
AUC _{0-last}	Area under the concentration-time curve from time 0 to the last measurable concentration
CD-1	Cluster of differentiation 1
CL	Clearance
C _{max}	Maximum serum concentration
CRO	Contract Research Organization
DBA	Dilute Brown Non-Agouti
DBP	Diastolic blood pressure
DMID	Division of Microbiology and Infectious Diseases
DSMB	Data Safety Monitoring Board
EC ₅₀	Half-maximal effective concentration
EDC	Electronic data capture system
GCP	Good Clinical Practice
GI	gastrointestinal
GLP	Good Laboratory Practice
HA	Hemagglutinin
HAI	Hemagglutination inhibition assay
HIV	Human immunodeficiency virus
ICF	Informed Consent Form
ICH	International Conference on Harmonization
IEC	Independent Ethics Committee
IgG1	Immunoglobulin G1
IRB	Institutional Review Board
ITT	Intent-to-treat
IV	Intravenous
LSLV	Last Subject Last Visit
MedDRA	Medical Dictionary for Regulatory Activities
mITT	Modified intent-to-treat
NOAEL	No-observed-adverse-effect level
NSAID	Non-steroidal anti-inflammatory drug
PK	Pharmacokinetic
PO	Oral (by mouth)
qRT-PCR	Quantitative reverse transcriptase polymerase chain reaction
SAE	Serious adverse event
SAP	Statistical analysis plan
SBP	Systolic blood pressure
SUSAR	Suspected unexpected serious adverse reaction
t _{1/2}	Elimination half-life
TCID ₅₀	Half-maximal tissue culture infective dose

Abbreviation	Definition

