4 GENERAL ANALYSIS DEFINITION

4.1 General Considerations

All statistical analyses and summary information are to be generated according to this SAP. Any deviations from this SAP will be documented in the CSR.

These descriptive statistics will be presented for continuous parameters: the number of subjects used in the calculation (n), mean, standard deviation (SD), median, minimum, and maximum values. For PK parameters, the geometric mean and coefficient of variance (CV) will also be presented. All continuous summaries will display the minimum and maximum value with the same number of decimals collected in the data. The median, mean, geometric mean and CV will display 1 additional decimal, and the SD and SE will display 2 additional decimals. For categorical variables, frequencies and percentages will be reported. All percentages will be reported to 1 decimal; all p-values will be reported to 3 decimals.

All temperature measurements will be presented as degrees Celsius. Degrees in Fahrenheit will be converted with this formula:

$$T_C = (T_F - 32) * (5/9),$$

where T_C is a Celsius temperature and T_F is a Fahrenheit measurement.

All statistical comparisons will be performed using 2-sided tests at the 0.05 significance level, unless specifically stated otherwise. All null hypotheses will be defined as no treatment difference. All p-values are presented for informational purposes only; there will not be any adjustments for multiple comparisons.

All analyses, summary tables, figures, and data listings will be generated with SAS version 9.4 or higher. Specialized PK software will be used for some PK analyses.

Baseline is defined as the latest non-missing measurement taken prior to study drug administration.

All summaries will be by actual visit, no visit windows for analysis will be defined. In general, summaries will be by treatment groups, and will include a combined VIS410 treatment group, in addition to the individual low dose (2000 mg) VIS410, high dose (4000 mg) VIS410, and Placebo treatment groups, unless specified differently. Summaries of disposition, other baseline data, and adverse events will also include an overall column.

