11.2 Nasopharyngeal Viral Load

Standard non-compartmental approaches using Phoenix WinNonlin (Pharsight Corporation, Princeton, NJ, USA; Version 7.0 or higher) will be used to calculate peak viral load (VL) and the area under the viral load-time curve (VL AUC). Viral load at each study visit, proportion of subjects with negative results at each study visit, peak VL, and VL AUC based on qRT-PCR and TCID₅₀ from nasopharyngeal secretions will be summarized with n, mean, SD, geometric mean, CV, minimum and maximum values in the mITT population overall and per influenza A virus subtype. All available viral data within the mITT population will be assessed to calculate proportion of subjects with negative results at each study visit. For all other calculated parameters, viral load will be assessed on all samples in the mITT population collected through the Day 7 visit. In addition, VL and VL AUC for the first 50 subjects will be listed through Day 14 (no summary statistics will be presented). For missing data on Day 3, Day 5 and Day 7, the analysis will be conducted without imputation and with the last observable measurement carried forward (LOCF). For missing data on Day 1, the analysis will be conducted by replacing the missing data with the Day 3 observable measurement. Subjects missing both Day 1 and Day 3 virology data will be removed from the analysis.

A t-test will be used to assess the difference between treatment groups in the VL AUC and peak VL from nasopharyngeal swabs based on qRT-PCR and TCID₅₀. If the assumptions needed for the t-test are not met, log transformation and/or non-parametric methods will be used.

Chi-square methods will be used to compare differences in treatment groups relative to placebo for the proportion of subjects with negative results on Day 3, Day 5 and Day 7 study visits.

A sensitivity analysis will also be performed; the data summary will be repeated in the mITT population excluding subjects who received antiviral therapy during the study. Determination of applicable antiviral therapy will be defined before the study is unblinded. All viral load data generated per the analytical plan will be listed.

For the influenza A virus subtype H3, virus load data measured by TCID₅₀ will be read out by both hemagglutination and NP-ELISA. The sensitivity is higher for NP-ELISA; therefore, all viral load parameters will be calculated using the data from NP-ELISA only.

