16.6.2 Listings

Listing	Title	Population
16.2.1.1	Subject Enrollment and Disposition Information	All Subjects
16.2.1.2	Listing of Subjects Who Terminated Early from the Study	All Subjects
16.2.1.3	Subject Inclusion and Exclusion Criteria Deviations	All Subjects
16.2.1.4	Analysis Populations	All Subjects
16.2.2	Protocol Deviations	All Subjects
16.2.3	Subjects Excluded from the mITT Population	Subjects Excluded from mITT
16.2.4.1	Demographics	ITT
16.2.4.2	Medical History	ITT
16.2.4.3	Prior Medications	ITT
16.2.4.4	Concomitant Medications	ITT
16.2.5.1	Pretreatment Medications	ITT
16.2.5.2	Study Medication Administration and Accountability	Safety
16.2.6.1.1	FluPRO Questionnaire and Compliance for Individual Questions and Total Symptom Scores by Mean and Sum	mITT
16.2.6.1.2	FluPRO Questionnaire Domain Symptom Questions and Symptom Scores by Mean and Sum	mITT
16.2.6.1.3	FluPRO Questionnaire Composite Symptom Questions and Symptom Scores by Mean and Sum	mITT
16.2.6.1.4	FluPRO Questionnaire Compliance Information	mITT
16.2.6.2	Patient Temperature Log	mITT
16.2.6.3	Influenza Complications and Relapse	mITT
16.2.6.4	Hospitalizations	mITT
16.2.7	Adverse Events	Safety
16.2.8.1	Hematology Laboratory	Safety
16.2.8.2	Chemistry Laboratory	Safety
16.2.8.3	Urinalysis Laboratory	Safety
16.2.8.3.1	Clinical Laboratory Test Results Outside the Reference Ranges	Safety
16.2.8.3.2	Subjects with >2 category shift in DMID grades	Safety
16.2.8.4.1	Vital Signs	Safety
16.2.8.4.2	Subjects who met PCS Vital Sign Criteria	Safety
16.2.8.5.1	Electrocardiogram Data	Safety
16.2.8.5.2	Subjects with QTcF Changes	Safety
16.2.8.6	Physical Exam Data	Safety
16.2.8.7	Individual Listing and Summary of Virus Type by Subject	All Subjects
16.2.8.8	Individual Listing and Summary of Serum VIS410 Concentrations by Nominal Time Point	PK
16.2.8.9	Individual Listing and Summary of Serum VIS410 Pharmacokinetic Parameters	PK
16.2.8.10	Individual Listing and Summary of Nasopharyngeal VIS410 Concentrations by Nominal Time Point	PK
16.2.8.11	Individual Listing and Summary of Nasopharyngeal VIS410 Pharmacokinetic Parameters	PK
16.2.8.12	Individual Listing and Summary of qRT-PCR by Nominal Time	mITT

Listing	Title	Population
16.2.8.13	Point Individual Subject Peak Viral Load (VL) and Area Under the Viral Load-Time Curve (VL AUC) Measured by qRT-PCR	mITT
16.2.8.14	Change from Baseline Viral Shedding [qRT-PCR] by Treatment Group	mITT
16.2.8.15	Individual Listing and Summary of TCID ₅₀ by Nominal Time Point	mITT

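### A missing pre-dose Day 1 viral load is replaced by the post-dose Day 3 value with no alternative analysis; if VIS410 lowers Day 3 load this exaggerates the peak difference and, slightly, the AUC difference

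*SAP*

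**What the plan says.** SAP 11.2 (viral load AUC and peak) gives this rule, and SAP 11.3 (time to resolution) repeats it: "For missing data on Day 1, the analysis will be conducted by replacing the missing data with the Day 3 observable measurement". If Day 3 is missing too, "Subjects missing both Day 1 and Day 3 virology data will be removed from the analysis".

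Protocol Table 1 schedules one pre-dose swab for viral load, with the footnote "Within 1 hour prior to VIS410 administration". The next swabs are on Days 3, 5 and 7 (each ±1 day). For AUC and peak, "viral load will be assessed on all samples in the mITT population collected through the Day 7 visit".

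Later visits are handled differently. For a missing Day 3, 5 or 7 value, "the analysis will be conducted without imputation and with the last observable measurement carried forward (LOCF"), so both versions are run. Day 1 has only the replacement. The one planned viral-load sensitivity analysis excludes subjects who received antivirals and leaves the Day 1 rule in place.

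AUC and peak are compared between arms: "A t-test will be used to assess the difference between treatment groups in the VL AUC and peak VL from nasopharyngeal swabs". SAP 4.1 says: "Baseline is defined as the latest non-missing measurement taken prior to study drug administration". SAP 16.6.2 plans a listing titled "Change from Baseline Viral Shedding [qRT-PCR] by Treatment Group" and a matching one for TCID50.

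**The concern.** The Day 1 value is the one viral load that randomised treatment cannot have influenced. Replacing it with a Day 3 value lets an outcome of treatment enter as if it came before treatment. If VIS410 reduces Day 3 load, the substitute is lower on VIS410 than on placebo, so the distortion differs by arm.

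Viral AUC, peak viral load and time to resolution are named secondary endpoints (SAP 3.2). The challenge-study results in Protocol 1.3 lead the sponsor to expect a viral effect. Because no version of the analysis omits the replacement, a reader of the results could not tell how much of an observed difference it contributed.

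**Working it through.** The plan gives no figure on this point to reproduce.

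**Inputs.** From the documents: swab days 1, 3, 5 and 7; 1:1:1 allocation of about 150 subjects, so about 50 per arm; the resolution definition (SAP 11.3); the mITT definition (SAP 5.1.2); the example limits of 2.18 and 0.75 (SAP 11.2.1). Not given, hence assumed: the share *m* missing Day 1 (2-20%, equal across arms), the log10 reduction *d* on VIS410 at each post-dose day, the load levels and the SDs. AUC is taken as a linear trapezoid on log10 load at nominal days.

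**AUC.** With 2-day intervals, AUC = V1 + 2·V3 + 2·V5 + V7 (log10 × days). V1 does not differ by arm on average.
- True arm difference: 2·d3 + 2·d5 + d7.
- With V1 set to V3: 3·d3 + 2·d5 + d7.
- Constant effect: 6d/5d = 1.20, a 20% inflation per affected subject. Overall, m × 20% = 1% at m = 5%, 2% at 10%, 4% at 20%.
- Effect on Day 3 only: 3/2 = 1.50. Overall, 2.5%, 5% and 10%.
- In hours with constant d = 1.0: true difference 5 × 24 = 120 log10 × h and excess 24 per affected subject, so 1.2 at m = 5% and 2.4 at m = 10%.

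**Peak.** The filled peak is max(V3, V3, V5, V7) = max(V3, V5, V7), so the fill-in itself changes nothing. When load is falling, an observed Day 1 value is usually the peak and is unaffected by treatment. A subject kept without Day 1 contributes a difference of about d3 instead. The excess is about m × d3: for d3 = 1.0, 0.05 log10 at m = 5% and 0.10 at m = 10%.

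**Time to resolution.** A subject still positive on Day 3 is unaffected. If Day 3 and every later sample are BLQ, the copied value moves resolution to Day 1, which is before the infusion. Timed from end of infusion, that is zero or negative.

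**Simulation.** Assumed: Day 1 mean 6.0 (qRT-PCR-like, limit 2.18) or 3.5 (TCID50-like, limit 0.75); fall of 1 log10 per visit; between-subject SD 1.3, within-subject SD 0.8; values below the limit set to zero, which simplifies SAP 11.2.1. Arm differences at d = 1.0 and m = 10%, first with mITT membership fixed regardless of the post-dose swabs:

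| | Full data | Day 3 rule |
|---|---|---|
| qRT-PCR-like AUC (log10 × days) | -5.768 | -5.880 (1.9% larger) |
| qRT-PCR-like peak (log10) | -0.107 | -0.206 |
| qRT-PCR-like resolution (days) | -0.478 | -0.492 |
| TCID50-like AUC | -3.963 | -4.059 (2.4% larger) |
| TCID50-like peak | -0.098 | -0.185 |
| TCID50-like resolution | -0.874 | -0.909 |

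If membership must come from the observed swabs, subjects without Day 1 who are qRT-PCR negative from Day 3 drop out. In the qRT-PCR-like case, full data against the Day 3 rule then give:
- AUC -5.72 against -5.69: the inflation is gone.
- Resolution -0.476 against -0.452 days: slightly against VIS410.
- Peak -0.100 against -0.157: the excess remains.

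With d = 0, bias is zero. Rejection rates (50 against 50, 2000 replicates, m = 5-20%) were 0.051-0.055 and 0.042-0.053 for the two assay types, which is 0.05 within simulation error.

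**Remedy tested.** Keeping only subjects with an observed Day 1 value (qRT-PCR-like, d = 1.0, m = 10%) gives AUC -5.69 (full data -5.72), peak -0.096 (full data -0.100) and AUC power 0.82 (full data 0.87). Dropping the fill-in while keeping the subjects would not be enough. Peak would be unchanged, and their AUC would cover Days 3-7 only, with difference d3 + 2·d5 + d7 = 4d against 5d.

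**The case against.** A reader might infer that the rule biases all three endpoints towards VIS410 whatever the truth. The documents do not support that.
- **Direction is conditional.** The rule magnifies a real Day 3 effect. It cannot create one, and the false-positive rate is unaffected.
- **Resolution is mostly untouched.** mITT requires central molecular confirmation. Under Protocol 7.1.5 the screening swab is for the rapid test, and the scheduled two-nostril swabs go to the central laboratory. A subject without Day 1 who is qRT-PCR negative from Day 3 would therefore ordinarily not be in mITT, although neither document says which specimen confirms infection. The problem is left mainly to TCID50, or to qRT-PCR values detected below the limit.
- **Change from baseline points the other way.** If the filled value entered those listings, the Day 3 change would be zero by construction, which hides a VIS410 effect. The SAP does not say that it enters.
- **The clash with SAP 4.1 is not a flat contradiction.** SAP 4.2 leaves special cases to the sections on each parameter, and SAP 11.2 never calls the filled value a baseline.
- **Few subjects may be affected.** The swab is taken in clinic within an hour of dosing, and subjects who cannot be swabbed are excluded (Protocol 4.4, criterion 4).
- **The stakes are limited.** There is no sample-size calculation, p-values are informational (SAP 4.1), and Protocol 1.1 says the sample does not support a statistically significant efficacy finding.

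All of this stands, and it limits scope and severity. It does not explain why Day 1 alone has no analysis without imputation, or make a post-dose value a sound substitute for a pre-dose one.

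**Conclusion.** The defect holds in limited form. A post-dose value replaces a missing pre-dose value in three secondary endpoints, and nothing planned would show its influence.

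Peak viral load is proportionally the most distorted. With a Day 3 effect of 1.0 log10 and 10% missing, the fixed-membership run adds about 0.10 log10 to a full-data difference of about 0.107. The cause is keeping subjects without Day 1. AUC inflation is about 1-2% at 5-10% missing under a constant effect, and may disappear depending on how mITT is confirmed. Time to resolution shifts by hundredths of a day on average (0.014 and 0.035 days in the fixed-membership runs at d = 1.0 and 10% missing), but the rule can date resolution to or before the infusion, which is impossible as a treatment outcome.

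These sizes rest on an assumed missing share and assumed viral trajectories; the documents give neither. Should-fix, because the endpoints are secondary and the p-values informational.

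**What to change.** Before unblinding, amend SAP 11.2 and 11.3:
- Delete the Day 3 back-fill for Day 1.
- Base the main AUC and peak analyses on mITT subjects with an observed pre-dose value. In a blinded trial, treatment cannot cause a swab to be missed before dosing, so this favours no arm. If the Day 3 rule is kept at all, label it as a sensitivity analysis.
- For time to resolution, keep subjects without Day 1, use only their observed post-dose samples, and do not let imputation date resolution to Day 1. Removing them would discard valid data, since time from end of infusion needs no Day 1 value.
- Carry no imputed value into the change-from-baseline listings (16.2.8.14 and 16.2.8.17).
- State which specimen confirms mITT membership, and report missing Day 1 counts by arm.

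The cost is SAP wording and some precision for AUC and peak: in the simulated case with 10% missing, AUC power was 0.82 against 0.87 with complete data.

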- $AUC_{0-\infty}$: area under the serum concentration-time curve from time 0 extrapolated to infinity
- $AUC_{0-\text{last}}$: area under the serum concentration-time curve from time 0 to the last measurable concentration
- $t_{1/2}$: terminal elimination half-life
- CL: total clearance
- V_d : volume of distribution

PK data from this study will be also analyzed by population PK modeling.

Nasopharyngeal Secretion Pharmacokinetics

Nasopharyngeal secretion concentrations and the computed PK parameters will be listed by subject for VIS410. Summary statistics of nasopharyngeal secretion concentrations and PK parameters will be presented including means, geometric means, standard deviations, CV, medians and ranges, as appropriate. Additional analyses and summaries may be generated as appropriate.

The following PK parameters will be determined for VIS410 from nasopharyngeal secretions:

- C_{\max} : maximum concentration observed from nasopharyngeal secretions
- T_{\max} : time of C_{\max}
- $AUC_{0-\infty}$: area under the nasopharyngeal secretion concentration-time curve from time 0 extrapolated to infinity
- $AUC_{0-\text{last}}$: area under the nasopharyngeal secretion concentration-time curve from time 0 to the last measurable concentration
- $t_{1/2}$: terminal elimination half-life
- Ratio of nasal:serum AUC

Additional PK parameters may be determined as appropriate.

9.3.4 *Viral Shedding*

Additional sensitivity analysis may be conducted excluding subjects that received concomitant antiviral therapy during the course of the study.

- One-way analysis of variance (ANOVA) (with treatment group as the factor) or other appropriate statistics detailed in the SAP to assess the difference between VIS410 treatment groups vs placebo in the area under the viral load-time curve (AUC) for influenza virus based on quantification of viral load from nasal swabs

- Descriptive statistics of the area under the viral load-time curve (AUC) for influenza virus based on quantification of viral load from nasopharyngeal swabs by treatment group.
- Descriptive statistics of the time to resolution of viral load and of the peak viral load by treatment group.

The mITT population will be used for the summaries.

9.3.5 *Signs and Symptoms of Influenza*

The difference between VIS410 and placebo will be assessed as outlined below.

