16.2.8.16	Individual Subject Peak Viral Load and Viral Load AUC Measured by TCID ₅₀	mITT
16.2.8.17	Change from Baseline Viral Shedding [TCID ₅₀] by Treatment Group	mITT
16.2.8.18	Immunogenicity Data - ADA	PK
16.2.8.19	Immunogenicity Data - HAI	mITT

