16.6.3 Figures

Figure	Title	Population
14.2.1	Kaplan-Meier Plot of Median Time to Normal Temperatures	mITT
14.2.2.1	Kaplan-Meier Plot of Median Time to Resolution of Domain Scores, Component Scores, and Total Score by Mean	mITT
14.2.2.2	Kaplan-Meier Plot of Median Time to Resolution of Domain Scores, Component Scores, and Total Score by 0 or 1	mITT
14.2.3.1	Kaplan-Meier Plot of Duration of Domain Scores, Component Scores, and Total Score by Mean	mITT
14.2.3.2	Kaplan-Meier Plot of Duration of Domain Scores, Component Scores, and Total Score by 0 or 1	mITT
14.4.1.1	qRT-PCR Median Viral Shedding versus Time Profiles	mITT
14.4.1.2	qRT-PCR Mean Viral Shedding versus Time Profiles	mITT
14.4.1.3	Individual Subject qRT-PCR Viral Shedding versus Time Profiles	mITT
14.4.1.4	TCID ₅₀ Median Viral Shedding versus Time Profiles	
14.4.1.5	TCID ₅₀ Mean Viral Shedding versus Time Profiles	mITT
14.4.1.6	Individual Subject TCID ₅₀ Viral Shedding versus Time Profiles	mITT
14.4.1.7.1	Duration of Viral Shedding Measured by qRT-PCR from End of Infusion (Days)	mITT
14.4.1.7.2	Duration of Viral Shedding Measured by qRT-PCR from Onset of Symptoms (Days)	mITT
14.4.1.8.1	Duration of Viral Shedding Measured by TCID ₅₀ from End of Infusion (Days)	mITT
14.4.1.8.2	Duration of Viral Shedding Measured by TCID ₅₀ from Onset of Symptoms (Days)	mITT
14.4.2.1	Mean Serum VIS410 Concentration versus Time Profiles (linear and log-linear scales)	PK
14.4.2.2	Mean Serum VIS410 Concentration versus Time Profiles (linear and log-linear scales) by ADA status	PK
14.4.2.3	Individual Subject Serum VIS410 Concentration versus Time Profiles (linear and log-linear scales)	PK
14.4.3.1	Mean nasopharyngeal VIS410 Concentration versus Time Profiles (linear and log-linear scales)	PK
14.4.3.2	Mean nasopharyngeal VIS410 Concentration versus Time Profiles (linear and log-linear scales) by ADA status	PK
14.4.3.3	Individual Subject Nasopharyngeal VIS410 Concentration versus Time Profiles (linear and log-linear scales)	PK

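### The planned comparisons of viral-load AUC and peak (SAP 11.2) make no adjustment for pre-dose viral load; the test is valid, but precision is lost to the extent that pre-dose viral load predicts the AUC

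*SAP*

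**What the plan says.** The SAP's test is: "A t-test will be used to assess the difference between treatment groups in the VL AUC and peak VL from nasopharyngeal swabs". It is applied to qRT-PCR and TCID50 results. If its assumptions fail, the fallback is log transformation or non-parametric methods. No covariate is named in either case.

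For AUC and peak, "viral load will be assessed on all samples in the mITT population collected through the Day 7 visit". The Protocol schedule (Table 1) places the Day 1 swab before dosing, and footnote 18 times it: "Within 1 hour prior to VIS410 administration". SAP 11.2 fills a missing Day 1 value with the Day 3 value, which confirms that Day 1 is part of both parameters.

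Protocol 9.3.4 names "One-way analysis of variance (ANOVA) (with treatment group as the factor) or other appropriate statistics detailed in the SAP". Its named model is therefore also unadjusted, but the SAP is free to choose another.

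The other planned viral-load analyses are:
- chi-square comparisons with placebo of the proportion negative at Days 3, 5 and 7 (SAP 11.2);
- Kaplan-Meier time to resolution, with a 95% CI about each median (SAP 11.3);
- univariable exposure-response analyses (SAP 11.5);
- by-visit summaries (SAP 11.2) and plots such as "qRT-PCR Mean Viral Shedding versus Time Profiles" (SAP 16.6.3).

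Baseline is used descriptively in two listings (SAP 16.6.2), for example "Change from Baseline Viral Shedding [qRT-PCR] by Treatment Group".

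**The concern.** The differences from placebo in viral AUC and peak viral load are named secondary endpoints (SAP 3.2). Subjects enter with different viral loads, and part of the spread in AUC is spread that was present before dosing. A t-test leaves that spread in the error term, whereas a model with pre-dose viral load as a covariate removes it. The trial already collects the covariate.

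What is at stake is the precision of a descriptive contrast. SAP 2.3 says there is no formal testing, and SAP 4.1 makes p-values informational, so the size of the difference and its uncertainty carry most of the information. SAP 11.2 names group summaries and a test, but no estimate or interval for the difference. The table shells are a separate document (SAP 16.7) and may add one. The same standard error drives the t-test and any such interval, so the loss applies either way.

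Peak viral load raises a second, conditional question. If viral load is already falling at dosing, the maximum over all samples is often the pre-dose value, and a comparison of peaks then says little about the drug.

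**Working it through.** **No figure to reproduce.** The documents state no SD, effect size, power or baseline-to-outcome correlation for viral load, and no sample-size calculation was done (SAP 2.4).

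**Inputs from the documents.** About 150 subjects randomised 1:1:1, so 150/3 = 50 per arm; two-sided 0.05; swabs at Day 1 pre-dose and Days 3, 5 and 7; dosing up to 72 hours after symptom onset (Protocol 4.3, criterion 6).

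**Assumed inputs.** 45 per arm in the mITT population (50 less 10%), and rho, the correlation of pre-dose viral load with AUC.

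**Step 1: share of the pre-dose swab in the AUC.** With swabs 2 days apart, the linear trapezoid gives weights in the ratio 1:2:2:1. The pre-dose value directly carries 1/6 of the total weight.

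**Step 2: validity.** With no drug effect, 50 vs 50 and 40,000 simulated trials (decline 0.75 log10/day), the t-test rejected in 5.2% of trials for AUC and 5.0% for peak. Type I error is held.

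**Step 3: CI width with adjustment.** For one dose against placebo (90 subjects in total), the ratio of adjusted to unadjusted width, including the lost degree of freedom, is

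sqrt((1 − rho²) × 88/87 × (1 + 1/86)) = sqrt((1 − rho²) × 1.0233)

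| rho | 1 − rho² | width ratio |
|---|---|---|
| 0 | 1.00 | 1.01 |
| 0.3 | 0.91 | 0.96 (0.965 unrounded) |
| 0.5 | 0.75 | 0.88 |
| 0.7 | 0.51 | 0.72 |

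**Step 4: what could make rho small.** In simulation the gain depends on whether subjects with higher baseline viral load also decline faster. The assumed grid was: baseline mean 6 log10 with SD 1.0 or 1.5; decline 0.4 or 0.7 per day; slope SD 0.35 or 0.5; residual SD 0.6, 1.0 or 1.5; floor at 0; no drug effect. Widths follow from the Step 3 formula.

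| correlation of baseline with rate of decline | rho | width ratio |
|---|---|---|
| 0 | 0.40–0.78 | 0.63–0.93 |
| 0.3 | 0.30–0.73 | 0.69–0.96 |
| 0.5 | 0.21–0.70 | 0.72–0.99 |
| 0.7 | 0.01–0.68 | 0.74–1.01 |

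The documents give no value for the first column. The gain can be substantial or close to nil.

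**Step 5: how often the peak is the pre-dose value.** Assumed: baseline SD 1.5, residual SD 0.7 or 1.0, slope SD 0.25.

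| mean decline, log10/day | pre-dose swab is the peak |
|---|---|
| 0 | 28–30% |
| 0.25 | 50–57% |
| 0.5 | 69–78% |
| 0.75 | 82–90% |
| 1.0 | 90–96% |

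The answer depends on the trajectory, which the documents do not describe for these patients.

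**Step 6: cost of dropping subjects without a Day 1 swab.** Losing 10% raises the standard error by sqrt(1/0.9) = 1.054. At rho 0.3, 0.965 × 1.054 = 1.017, so the gain is gone. At rho 0.5, 0.876 × 1.054 = 0.923, so part of it remains.

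**The case against.** The strongest case against is that this is a preference between two valid methods in a Phase 2a safety study. Its size was not calculated, its p-values are informational, and Protocol 1.1 says the sample does not support a statistically significant determination of efficacy. The SAP's t-test is also consistent with the protocol's one-way ANOVA. All of that stands. It makes the change optional, but it does not remove the precision that adjustment could recover.

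It is also fair to say that the size of the gain is unknown. The gain is conditional on rho and shrinks if higher-baseline subjects decline faster. A reader might infer from favourable simulations that adjustment would greatly raise power. The documents do not support that, because every input is assumed and the simulated ranges are not bounds.

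A reader might also infer that the plan has no comparison of post-dose virology apart from peak. It has two: the chi-square comparisons at Days 3, 5 and 7, and the Kaplan-Meier time to resolution, which is derived from end of infusion as well as from symptom onset. Both address post-dose clearance, and neither depends on which swab is the peak. What they do not provide is a baseline-adjusted comparison of AUC.

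**Conclusion.** The point holds as an optional improvement. SAP 11.2 compares AUC and peak by an unadjusted test on parameters that include the pre-dose swab, and no planned viral-load comparison uses baseline viral load as a covariate. Precision on AUC is lost to the extent that pre-dose viral load predicts it. At an assumed 45 per arm, the adjusted interval would be about 0.96, 0.88 and 0.72 of the unadjusted width at rho 0.3, 0.5 and 0.7, and about 1% wider at rho 0.

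Two stronger readings should be resisted. The first is that the t-test is biased or would give a wrong conclusion. Randomisation balances pre-dose viral load in expectation, and the simulated error rates are nominal. The second is that peak viral load is mostly a pre-dose value. Entry up to 72 hours after onset makes a falling viral load plausible, but the documents do not show it, and with a flat course the pre-dose swab is the peak in only about 3 subjects in 10.

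**What to change.** In SAP 11.2, compare viral-load AUC by ANCOVA with treatment and pre-dose log10 viral load on the same assay. Report the adjusted difference with a 95% CI for each dose and for combined VIS410 against placebo, which are the contrasts that Protocol 9.3 calls for. Name rank ANCOVA as the non-parametric fallback, because SAP 11.2.1 sets negative and repeated below-limit values to zero. Keep the t-test and peak viral load as supportive.

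The covariate must be a true pre-dose value, in line with the baseline definition in SAP 4.1. The Day 3 back-fill in SAP 11.2 is a post-dose value and must not serve as the covariate. Handle a missing baseline by treatment-blind imputation rather than by dropping subjects, since a 10% loss would cancel the gain at rho 0.3.

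A baseline-adjusted maximum over Days 3, 5 and 7 could be added, but only as exploratory. It is not a protocol endpoint, and under steady decline it is largely the Day 3 value.

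The cost is SAP wording before unblinding, some programming for each assay and contrast, and one degree of freedom. No new data are needed, and Protocol 9.3.4 already lets the SAP choose the method.
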